### **Specific Aim 3.**

#### The third specific aim will determine whether the effectiveness of MBRP vs. RP on clinical outcomes is mediated by the effect of MBRP on molecular mechanisms, and, in turn, their effects on network connectivity and BOLD response.

- Hypothesis 4. It is hypothesized that the effects of MBRP on clinical outcomes (Hypothesis 1) will accrue through two routes: the effects of MBRP on reductions in inflammatory markers

(Hypothesis 2) which in turn influence LECN/RECN connectivity; and the effect of MBRP on methylation of key genes which in turn influence cue-elicited BOLD activation in the striatum (Hypothesis 3). These effects will be tested in the context of a structural equation modeling framework.

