### **Power for Specific Aim 1 - Detecting Treatment Effects on Alcohol Use Outcomes.**

The analyses of treatment effects will proceed via random coefficient regression utilizing a 2 (**Treatment**: 8 weeks of MBRP vs. 8 weeks of RP) x 5 (**Time**: Baseline, 4, 8, 20, 32 weeks) mixed general linear model. The primary outcome variable tested will be heavy drinking days (HDD), consistent with previous MBRP trials ([name] et al., 2014). Secondary analyses will explore related outcomes such as drinks per drinking day, scores on the ICS, and liver function tests, with appropriate control of Type I error. In each model, the key effect of interest will be the treatment X time interaction. Given the effect sizes in previous trials (small  $d=.23$  or  $f<.10$  to moderate  $d=.45$  or  $f=.20$ ), we conservatively estimate a small effect size (e.g.,  $f=.10$ ). A mixed model testing the between (treatment) X within (time) subjects interaction with a total of 180 participants (90 per treatment group) will give us well over .90 power, assuming alpha of .05 and a correlation of approximately .50 between repeated assessments. Given that we expect 20% attrition over the course of the trial, we will initially recruit ~226 participants.

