### **Power for Specific Aim 3 – Mediational Analysis.**

Aim 3 will involve a test of the hypothesis that the effectiveness of MBRP vs. RP on clinical outcomes is mediated by the effect of MBRP on the molecular mechanisms, and, in turn, their effects on network connectivity and BOLD response. This analysis will involve the use of structural equation modeling ([name] et al., 2007) techniques of the mediational model posited in Figure 4. Based on our review of the literature (see above for details and effect sizes), we expect moderate to large paths ( $d=.60$ ) for the effect of MBRP on epigenetics and inflammation. We expect small to moderate relationships between epigenetics and cue-elicited BOLD activation and between inflammation and network connectivity strength ( $d=.30$ ). Finally, for paths relating BOLD activation and network connectivity strength to drinking outcomes we expect paths in the small to moderate range ( $d=.30$ ). We expect moderate to large ( $d=.75$ ) loadings of all indicators for their respective latent constructs (for example, the loadings of heavy drinking days, drinks per drinking day, and impaired control on the Drinking Outcomes latent variable). Power analyses for these hypotheses were conducted in Mplus and then in SAS following procedures for estimating the power of the likelihood ratio test of the significance of parameters in structural equation models (Muthén & Muthén, 2002). We utilized Monte Carlo simulation to generate a population covariance matrix based on the hypothesized

parameters in the model. For the smallest path in the model, assuming two-tailed alpha of .05, our power to detect a significant parameter estimate is .71 with 150 participants and .83 with 200 participants; with 226 participants we have .87 power. For the moderate to large paths, we have well over .99 power with 226 participants.

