### **Specific Aim 3 - Mediational analyses.**

Mediational analyses based on structural equation modeling with latent variables will be used to examine the mechanisms by which MBRP has its effects on behavioral outcomes related to alcohol use and dependence (See Figure 4; HYPOTHESIS 4) (Baron & Kenny, 1986; [name] et al., 2007). Mediational analyses will utilize the methylation and inflammation data collected at 4 weeks, and changes in cue-elicited BOLD activation and network connectivity strength at 8 weeks as the mediators, and drinking outcome data collected at 20 weeks. The exogenous variable in the model is the contrast that compares MBRP to RP. Methylation, inflammation, and drinking outcomes are all conceptualized as latent variables, which means that they are not directly measured, but are rather inferred via the measurement of variables thought to be a consequence of the latent variable. Latent variables have advantages over measured variables in that they are more reliable and thus allow for higher power for the test of relationships between the underlying construct and other variables (Kline, 2010).

The model is then estimated in EQS, and both the fit of the model and the significance of the path coefficients are examined. If HYPOTHESIS 4 is supported, we will see significant paths from the treatment contrast to methylation and inflammation. Further, there will be significant paths from methylation to cue-elicited BOLD activation and from inflammation to network connectivity. Finally, we expect significant relationships between BOLD activation and network connectivity to drinking outcomes. Importantly, tests for the completeness of mediation of the treatment differences in drinking outcomes are employed through a one degree of freedom  $\chi^2$  test where a path directly from the treatment contrast to drinking outcomes is added to the model. A nonsignificant direct path and a nonsignificant change in  $\chi^2$  suggest that treatment effects on drinking outcomes were mediated through the series of molecular and brain-based mechanisms. A secondary test of mediation will utilize bootstrap methods to test the significance of, and confidence limits around, the mediated effect (Mackinnon & Dwyer, 1993). Similar mediational analyses have been widely used by Co-I [name] ([name] et al., 2007).

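### Aim 3 reads a nonsignificant direct path as a sign that the treatment effect was mediated; if the effect on drinking is small, that result cannot separate complete from half mediation.

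*Combined protocol and SAP*

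**What the plan says.** Hypothesis 4 (Objectives, Specific Aim 3) holds that the clinical benefit of the experimental arm "will accrue through two routes: the effects of MBRP on reductions in inflammatory markers", leading to executive-network connectivity, and a second route through methylation to cue-elicited BOLD response.

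The Data Analysis Plan, under Specific Aim 3 - Mediational analyses, sets out three pieces of evidence:

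- If Hypothesis 4 is supported, six paths should be significant: treatment to methylation and to inflammation, each of these to its brain measure, and each brain measure to drinking.
- A path from treatment straight to drinking is added and tested by chi-square on 1 df. The plan gives its purpose in these words: "tests for the completeness of mediation of the treatment differences in drinking outcomes are employed through a one degree of freedom". If neither the added path nor the chi-square change reaches significance, the results are taken to "suggest that treatment effects on drinking outcomes were mediated through the series of molecular and brain-based mechanisms".
- Bootstrapping, ranked as secondary, supplies a significance test and confidence limits for the indirect effect.

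The section asks for no interval on the direct effect, sets no bound below which it would count as negligible, and does not say whether the bootstrapped effect is the total or is given for each route. Power for Specific Aim 3 covers only the modelled paths, not the direct one.

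**The concern.** The plan calls the direct-path step a test of completeness and then treats failure to reject as support for a statement about the treatment effect as a whole. The two conditions do not corroborate each other: the z-test of one added path and the 1-df chi-square change are essentially the same test.

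A nonsignificant result is informative only if the test would probably have detected a direct effect of a size that matters. If it would not, a report that follows the plan could attribute the effect of MBRP on drinking to the molecular and brain routes when a large part bypassed them. Identifying mechanisms is the purpose of Aim 3, and the Background proposes to use them to refine treatment and to build early tests of response. The primary analysis of heavy drinking days is not affected.

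**Working it through.** **Inputs.** Two-sided alpha .05 (Sample Size Requirements). 180 analysed, 90 per arm, and about 226 recruited, 113 per arm (Power for Specific Aim 1; Objectives). Effect on drinking: previous trials d = .23 to .45, with the statement that "we conservatively estimate a small effect size", f = .10, which is d = 2f = .20. The share of the effect left unmediated is not in the documents; I show none, half and all.

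**The plan's own figures.** For the Aim 1 interaction, lambda = f² × N × m / (1 − rho) = .01 × 180 × 5 / .50 = 18, on 4 and 712 df. Power is .94, which agrees with the stated well over .90. Attrition: 180 / .80 = 225, against about 226.

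**Precision of the direct effect.** I treat the direct path as a two-group contrast in SD units.

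- 95% half-width = 1.96 × √(2/n): .292 at n = 90 and .261 at n = 113. Both exceed .23.
- Direct effect needed for 80% power = (1.96 + .84) × √(2/n): .42 and .37, about twice the planned small effect.

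**Chance of a nonsignificant direct path.** Noncentral t on N − 2 df, with noncentrality (unmediated share × d) / √(4/N).

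| Total d | N | No direct effect | Half unmediated | None mediated |
|---|---|---|---|---|
| .20 | 180 | .95 | .898 | .734 |
| .20 | 226 | .95 | .884 | .678 |
| .23 | 180 | .95 | .880 | .664 |
| .23 | 226 | .95 | .862 | .594 |
| .45 | 180 | .95 | .677 | .149 |
| .45 | 226 | .95 | .609 | .080 |

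At d = .20 to .23 the likelihood ratio for half unmediated against no direct effect is .862/.95 = .91 to .898/.95 = .95. Seeing a nonsignificant path hardly shifts the odds between the two.

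**Checks on the approximation.**

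- A simulated two-route path model with a 1-df likelihood-ratio test gave, for direct effects of 0, .10 and .20, .948/.886/.684 at N = 180 and .947/.867/.620 at N = 226. With outcome reliability .79 (three indicators loading .75) it gave .948/.897/.749 and .946/.894/.697.
- If the model also adjusts for baseline drinking at a correlation of .50, the half-width is multiplied by √.75, giving .253 and .226: still about the size of the whole effect. The none-mediated figures at d = .20 to .23 become 49 to 66%.

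**What the documents do not fix.** Power for Specific Aim 3 labels its path sizes d: .60 for treatment to mediator, .30 for the later links, and .75 for the "loadings of all indicators for their respective latent constructs".

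- Read as standardised paths, the two routes carry 2 × .60 × .30 × .30 = .108, about half of d = .20.
- With .30 converted to a correlation of .148, they carry 2 × .60 × .148² = .026.
- The stated powers of .71, .83 and .87 fit a path of about .2055, since Φ(.2055 × √N − 1.96) = .711, .828 and .871 at N = 150, 200 and 226. The routes then carry 2 × .60 × .2055² = .051. Treating the paths as independent and observed, all six would be significant in about .787⁴ × .981² = 37% of trials at N = 180 and .871⁴ × .995² = 57% at N = 226.

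**The case against.** *The direct path is not the criterion for Hypothesis 4.* Correct. The plan ties support for that hypothesis to the six paths, and that protects well: in a latent-variable simulation, six significant paths with a nonsignificant direct path occurred in at most 0.5% of trials when a link was absent. A reader might infer that the plan would declare mediation where there is none; the documents do not support that. Six significant paths show that something is mediated. They do not limit the remainder, which is what a completeness test addresses.

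*The wording is only that the result suggests mediation, and does not say full mediation.* The hedge is real, but the plan itself names the step a test of completeness.

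*The effect may not be small at week 20.* This stands in part. The f = .10 belongs to a treatment-by-time interaction over five visits. Under compound symmetry, lambda = (90/2) × Σ(δ − mean δ)² / .50 = 18. A difference sustained from week 4 makes the sum .8d², so 72d² = 18 and d = .50. Linear growth across visits, δ = 0, c, 2c, 3c, 4c, gives 900c² = 18, c = .141, and d = .42 at week 20. At such values the test separates the cases much better. Still, Power for Specific Aim 1 pairs d = .23 with f below .10 and calls its choice small, so .20 to .23 is a fair reading.

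*The bootstrap is already planned; promote it to the primary test.* That is tempting but unnecessary. With the .30s read as standardised paths, intervals for both routes excluded zero in about 78% (N = 180) and 92% (N = 226) of simulated trials at d = .20. The six-path rate implied by the same simulation is about the same: .716/.905 = .79 and .840/.907 = .93. The order of the tests does not touch the fault.

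**Conclusion.** The concern holds for the completeness inference. If the effect on drinking is d = .20 to .23, a nonsignificant direct path is about as likely with half the effect unmediated (86 to 90%) as with no direct effect (95%), and it is the usual result even with nothing mediated (59 to 73%). At d = .45 the figures are 61 to 68% and 8 to 15%: the test is then useful against no mediation, but still weak against half.

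These figures rest on d = 2f, on a direct path estimated about as precisely as a two-group contrast, and on 180 to 226 participants with mediator data. Participants without scans or blood would, if anything, widen the interval.

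Two stronger statements might be inferred and are not supported. One is that about half the effect will in fact be unmediated: the share follows from how the path sizes are read (.026 to .108 SD through the routes), and the documents do not settle that. The other is a fixed rate at which the plan would wrongly report mediation: it depends on the same reading, and no single rule in the plan combines the six paths with the direct path.

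**What to change.** In the Data Analysis Plan, Specific Aim 3 - Mediational analyses:

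1. Replace the sentence on nonsignificance with: *A nonsignificant direct path or chi-square change is not evidence of complete mediation; we claim only that an indirect effect is present and describe the unmediated remainder by its confidence interval.*
2. Report the direct effect with its 95% confidence interval beside the bootstrap interval for the mediated effect, and give the latter for each of the two routes in Hypothesis 4.

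The primary and secondary order of the mediation tests can stay as it is. The cost is a sentence and one more reported interval, with no new data or participants. The downside is that complete mediation will rarely be claimable, which is what this sample size can support.

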### **Exploratory Aim 1.**

We will also conduct an additional exploratory analysis comparing populations of microbial DNA pre and post-intervention. We will control for age, gender, and diet, because these factors can differentially influence the gut microbiome as well. To do this, we will run a series of OLS multiple

regression models regression microbiome values on age, gender, fruit and vegetable consumption, and the contrast coded intervention (MBRP or RP) group variable both pre and post intervention. A follow-up analysis may include looking within an intervention group, and regressing age, gender, fruit and vegetable consumption and a continuous measure of alcohol use (i.e., total AUDIT score or TLFB drinks per drinking day) on the microbiome values to determine whether there is a dose-response relationship between alcohol intake and changes to the microbiome. We will also explore interactions between changes in the gut microbiome and changes in inflammation and liver function.

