### **Specific Aim 1.**

#### Comparing the effectiveness of MBRP (n=113) to RP (n=113).

- Hypothesis 1. It is hypothesized that MBRP will demonstrate superior effectiveness, as compared to RP, by reductions in heavy drinking days at the end of treatment (8 weeks) and longer term (20 and 32 weeks) decreases in liver function tests (8, 20, and 32 weeks).

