### ***Gut Microbiome Sample Collection and Microbial DNA Extraction:***

#### **Fecal Sample Collection, Storage, Extraction, and Sequencing (Baseline, Week 8)**

We expect to see changes in both the number and diversity of microbiota populations found in the gut as a result of treatment and reduced alcohol consumption. Because inflammation, liver function, and the gut microbiome are heavily intertwined, we will examine the relationship between changes in the gut microbiome with changes in inflammatory biomarkers in the blood (cytokines and blood monocyte cell response to LPS challenge) and liver function as a result of both RP and MBRP therapy. Fecal samples will be collected from participants using at-home kits and then stored at -80°. Microbial DNA will be extracted from fecal samples and then analyzed to determine how many and which bacterial species are present in the gut. Gut microbiome data will be collected at baseline and 8 weeks so that we can monitor changes in number and diversity of microbial DNA pre and post-intervention.

Due to the COVID-19 situation we are collecting remote data only and will return to our original protocol when it is safe to do so. The remote RESEARCH STUDY DESIGN will be as follows:

Because of the remote nature of the study, we will not be collecting the data mentioned above: MRI data, microbiome samples, or blood data.

We will be administering the parts of this study that can be done remotely through contact with a research assistant: All therapy sessions (mentioned above), and the Validating Self-report Measures listed directly below.

Additionally, due to the necessity of the remote nature attributable to COVID: All participants will need access to the internet whether by computer, smartphone, or other device such that they can complete this study. A research assistant will send unique links to participants that they will simply click on in order to participate, applications such as: Zoom (an internet application that allows us to see

and talk with the participant), Qualtrics and REDCap (online survey platforms), and DocuSign (an internet application that allows us to send forms for signatures).

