Subjects will then complete baseline questionnaires related to their demographics, history of drinking, smoking and drug use, and alcohol craving (measures listed below). Also, subjects will take six neurocognitive tests using the NIH toolbox application, which will assess their cognitive function in terms of memory and attention. If not eligible for the MRI, subjects will be randomly assigned to receive MBRP or RP for the next 8 weeks at the end of their baseline session and will also be given their microbiome sample collection kits at the end of the session. They will return the sample kits at their next scheduled session. Subjects will be compensated \$30 for completion of the baseline appointment.

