#### ***Microbiome and Alcohol Data Sharing:***

We plan to generate approximately 150 human gut microbiota metagenomes (i.e., microbiome). Per NIH policy of Genomic Data Sharing for this number of samples of non-human genetic data generated, data will be broadly shared for participants who consent. Specifically, de-identified gut metagenome data and phenotype data for consenting participants will be shared through GenBank, an NIH genetic sequence database at the National Center for Biotechnology Information that provides an annotated collection of publicly available DNA sequences. Data submission to GenBank will include individual-level microbiome data and phenotypic data related to alcohol use and depression. Separate signatures will be obtained for permission to broadly share these data.

---

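### Exploratory Aim 1: the optional alcohol-microbiome dose-response follow-up is framed within an intervention group, so each fit uses about half the participants and cannot test whether the slope differs by arm

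*Combined protocol and SAP*

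**What the plan says.** The Exploratory Aim 1 paragraph of the Data Analysis Plan describes two steps.

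- **Main models.** OLS regressions of microbiome values on age, gender, fruit and vegetable intake and "the contrast coded intervention (MBRP or RP) group variable both pre and post intervention". These use both arms.
- **Follow-up.** "A follow-up analysis may include looking within an intervention group", with the same three covariates and a continuous alcohol measure (AUDIT total or drinks per drinking day from the Timeline Follow Back). Its purpose is "to determine whether there is a dose-response relationship between alcohol intake and changes to the microbiome".

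The follow-up sentence does not say which arm is meant, whether one arm or each arm in turn, whether baseline or week 8 is used, or why the arms are separated.

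Sampling makes no distinction by arm: "Gut microbiome data will be collected at baseline and 8 weeks" (Fecal Sample Collection). Section XI (Procedures) gives the stool kits, the Timeline Follow Back, the AUDIT and the fruit and vegetable screener to participants in both arms. On numbers, the data-sharing section says "We plan to generate approximately 150 human gut microbiota metagenomes". It does not say whether that counts people or samples. The COVID-19 text at the end of the microbiome subsection in section IV says that no microbiome samples are collected in the remote phase.

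**The concern.** How drinking relates to the gut microbiome is not, on its face, a question about one therapy. The first step of the same paragraph uses both arms with an arm term; the second step drops that structure without explanation.

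Two things are at stake. The first is precision: allocation is 1:1, so a within-arm fit has half the participants. The second is interpretation: a within-arm fit, or a pair of them, has no term that tests whether the slopes differ. If both arms were fitted separately, a reader could take a p-value below .05 in one arm and above it in the other as evidence of a difference, which it is not.

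The restriction is hardest to justify at baseline. That kit is due back at the goal-setting session, before the weekly therapy sessions start.

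**Working it through.** **No figure to reproduce.** The documents give no sample size, effect size or power for this follow-up. The only figure that can be checked is the overall sample base: 180 / (1 − 0.20) = 225, against the stated recruitment of about 226, which agrees.

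**Inputs from the documents**
- 113 per arm, 226 in total (Specific Aim 1)
- 180 after 20% attrition, 90 per arm (Power for Specific Aim 1)
- About 150 metagenomes (Microbiome and Alcohol Data Sharing)
- Two-sided alpha .05 and power of at least .80 (Sample Size Requirements, a general statement)

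**Assumptions**
- A partial correlation r of .20 between alcohol measure and microbiome value. This is illustrative only.
- Four values of N: 226, 180, 150 (one metagenome per person) and 75 (150 metagenomes at two per person).
- A slope common to both arms, for the pooled figures.

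**Formulas (Fisher z)**
- SE = 1/√(n − k − 3). In one arm k = 3 (age, gender, diet), so SE = 1/√(n − 6). Pooled, k = 4 (plus arm), so SE = 1/√(N − 7).
- Smallest r detectable at 80% power = tanh[(1.960 + 0.842)/√(n − k − 3)].
- Power = Φ[atanh(r)·√(n − k − 3) − 1.960], with atanh(.20) = 0.2027.

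**Worked case, N = 150**
- One arm, n = 75: √69 = 8.307; 0.2027 × 8.307 = 1.684; Φ(1.684 − 1.960) = .391. Detectable r = tanh(2.802/8.307) = .325.
- Pooled, N = 150: √143 = 11.958; 0.2027 × 11.958 = 2.424; Φ(2.424 − 1.960) = .679. Detectable r = tanh(2.802/11.958) = .230.
- SE ratio = √(143/69) = 1.44.

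**All cases**

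| N total | n in one arm | SE ratio, one arm / pooled | Detectable r, one arm | Detectable r, pooled | Power at r = .20, one arm | Power at r = .20, pooled |
|---|---|---|---|---|---|---|
| 226 | 113 | √(219/107) = 1.43 | .264 | .187 | .555 | .851 |
| 180 | 90 | √(173/84) = 1.44 | .297 | .210 | .459 | .760 |
| 150 | 75 | √(143/69) = 1.44 | .325 | .230 | .391 | .679 |
| 75 | 37 | √(68/31) = 1.48 | .465 | .327 | .203 | .387 |

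**Sensitivity to r.** At N = 150, power in one arm against pooled is .564 against .863 for r = .25, and .729 against .959 for r = .30.

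**Limit of the remedy.** Take 75 per arm and partial correlations of .20 in one arm and 0 in the other. The standardised difference is 0.2027/√(2/69) = 1.19, so power for the interaction is about Φ(1.19 − 1.96) = .22. The interaction test would rarely settle whether the slopes differ.

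**The case against.** The strongest case against the point has four parts.

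- **Status.** The plan says the follow-up may be done, under an exploratory aim, after a main model that already uses both arms. Hypothesis 5 concerns differences between arms, not dose-response. This stands and keeps the point minor, but it supplies no reason for the restriction.
- **Discarded data.** A reader might infer that the plan commits to analysing one arm and throws away half the sample. The documents do not support that. The step is optional, and the wording can equally mean each arm in turn, in which case nothing is discarded. Each slope would still rest on about half the participants.
- **Slopes may differ after treatment.** The protocol expects MBRP to lower inflammation and treats inflammation, liver function and the microbiome as closely linked, so a week 8 slope could depend on arm. An arm term removes a difference in means, not in slopes. This stands: the pooled gain applies to a common slope, and arm-specific slopes keep roughly one-arm precision in any model. It argues for an interaction term at week 8 and has no force at baseline.
- **Invented numbers.** N and r are not given for this analysis, and the 150 comes from a data-sharing statement. This also stands, which is why a range is shown. The 180 applies attrition for the whole trial although stool sampling ends around week 8, so it may be too low on that count. The absence of samples in the remote phase pulls the other way, by an unstated amount.

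Nor does the plan announce any comparison of separately fitted slopes. The risk of misreading two p-values is a possibility left open by the wording, not a planned error.

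**Conclusion.** The point holds as a minor improvement to an optional exploratory analysis. Whether one arm or each arm in turn is meant, a within-arm regression uses about half the available participants, has a standard error about 1.43 to 1.48 times that of a pooled fit, and cannot test whether the slope differs by arm. At an assumed partial correlation of .20, power falls from between .387 and .851 pooled to between .203 and .555 in one arm, over N from 75 to 226.

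These figures rest on assumed values of N and r, equal arms, and a common slope for the pooled fit; N may be lower because of the remote phase. They illustrate the relative loss. They do not show that the trial is underpowered for any stated hypothesis, because no stated power figure or confirmatory conclusion depends on this follow-up.

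**What to change.** Reword the follow-up sentence so that, if the analysis is run, it is one regression on both arms with the microbiome value as outcome and alcohol measure, arm, age, gender and fruit and vegetable intake as predictors. Stating the outcome also settles the present wording, which regresses the predictors on the microbiome values.

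- **Baseline:** the common slope is the target.
- **Week 8:** add an arm-by-alcohol term as the check on pooling.
- **Arm-specific slopes:** report them from that same model as descriptive only, with a note that the interaction test has low power and that a non-significant result does not show equal slopes.
- **Sample size:** state whether the approximately 150 metagenomes are people or samples.

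The cost is a change of wording, one degree of freedom for arm, one more for the interaction at week 8, and a common-slope assumption for the pooled estimate. No new data or visits are needed, and within-arm estimates remain available.
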